3. Study Significance: This study will hopefully provide evidence that Doula enhanced care improves the quality of the healthcare process through improved communication and satisfaction for Black birthing people (primary outcome). In addition, we hope to show Doula enhanced care will improve specific disparities for Black birthing people including cesarean delivery, preterm birth, postpartum depression, and breastfeeding rates (our secondary outcomes). If our study is successful in showing these improvements in birth equity, we will submit an NIH (National Institutes of Health) R01 proposal to conduct a large-scale study on Doula enhanced care to improve the quality of health care for all birthing people. Black mothers have increased risk of cesarean delivery, preterm birth, postpartum depression, and lower rates of breast feeding (1). Poor pregnancy outcomes among Black-birthing people are multifactorial. Doula support during pregnancy and childbirth is associated with improved engagement and communication with the healthcare team, increased satisfactions with the birth experience, and decreased maternal stress (2,3). These factors may explain why Doula support has also proven to lower rates of cesarean delivery, preterm birth, postpartum depression and improve breast feeding rates (3,4,5).
4. Literature Review: Several studies suggest doula services help address birth inequities. First, doula services for pregnant people at risk of poor birth outcomes because of low-income or racial diversity may help disrupt influence of social determinants as predisposing factors for health during pregnancy and childbirth. Second, doula supported people have shortened labor and a decreased need for cesarian deliveries and other high-

risk procedures. They also rate childbirth as less difficult and painful than those without support. This can lead to lowering costs of care for pre-term and cesarian sections. Furthermore, doula services may also facilitate a higher rate of breast feeding.

C. Rationale

1. Based on associations between Doula enhanced care and reductions in cesarean delivery and preterm birth, coverage reimbursement for Doula services have proven to be cost-effective (6). However, there are significant socioeconomic, structural, and systemic barriers to Doula access, often preventing the most vulnerable patients from receiving Doula enhanced services.

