2. By better understanding if Doula enhanced care improves communication and quality of maternal care, we can begin to understand how to improve maternal care for Black birthing people. Also, by having Doula enhanced care available, we might reduce the chances of cesarean delivery and preterm birth and increase the likelihood of breastfeeding.

II. Research Plan and Design

A. Study Objectives:

1. The primary objective of the study is to demonstrate improved perceived communication and quality of maternal care among Black birthing people with Doula enhanced care compared to routine pregnancy care at the University of Kansas Health System. This study's primary outcome is to provide evidence that Doula enhanced care improves communication and satisfaction for Black-birthing people by improving the quality of healthcare with the addition of Doula enhancement to the health care team. In addition, the secondary outcome is to show how Doula enhanced care will improve specific disparities between Black birthing people and their White counterparts, including cesarean delivery, preterm birth, postpartum depression, and breastfeeding rates.

B. Study Type and Design:

This study will be an interventional randomized control trial that will have a control group and an experimental group. These groups will be randomly assigned at the patient's enrollment into the study.

C. Sample size, statistical methods, and power calculation

1. Two test Run patients will receive Doula Care from [name]. This will consist of two prenatal visits.
2. Randomization will be 1:1 and will stop after reaching our desired sample size of forty total patients. Forty patients will be enrolled in the study. Twenty patients will receive Doula enhanced care and Twenty patients will receive routine pregnancy care.

D. Subject Criteria (See Vulnerable Populations appendix, if applicable):

1. Inclusion criteria:

- a. Black birthing people receiving prenatal care with planned delivery at University of Kansas Health System between the ages of 16 and 50 years old.
 - i. Parental consent is not required for minors less than 18 years old because this study is directly related to their pregnancy.
- b. A positive social determinants of health screen.

- c. Patients must have an estimated gestational age of at least 14 weeks, but less than 28 weeks (27.6) when enrolled in the study.

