5. Data will be linked to subjects with an alphanumerical identifier and will only include pertinent PHI (Protected Health Information) for the study.
6. Data will be stored and protected in RedCap
7. Clinical Research Coordinator may consent patients over the phone and with a link to the Redcap survey. Coordinator may use a physical paper copy of the consent, or an iPad provided by KUMC to link directly to the Redcap Survey.
8. No data sent outside KUMC.

B. Procedures to protect subject confidentiality:

1. Data will be kept securely in research databases, password protected, and de-identified. Participants will be assigned a random alphanumerical study ID to associate survey responses with the data.

C. Quality Assurance / Monitoring

1. Self-assessment will be used to assure the data collected are accurate, consistent, complete, and dependable.
2. No plans to have ongoing third-party monitoring.

V.Data Analysis and Reporting

A. Statistical and Data Analysis:

1. The department of OBGYN statistician will perform all statistical analysis. For the primary and secondary outcomes, t-tests will be used to compare continuous variables and chi-squared tests will be used to compare categorical variables. Risk ratios will be computed using simple logistic regression and 95% confidence intervals will be reported. Qualitative questions will be coded, and common themes will be identified.

B. Outcome:

1. Our primary objective is to demonstrate improved perceived communication and quality of maternal care among Black birthing people with enhanced Doula enhanced care compared to routine pregnancy care at the University of Kansas Health System. We will use quantitative surveys to assess satisfaction and perceived quality of prenatal, labor and delivery and early postpartum care.

C. Study results to participants: Participants will receive a letter with the study results.

D. Publication Plan: If successful in improving pregnancy care with an increase in perceived quality of care and reduction adverse pregnancy outcomes, we will use our results to write a pilot study and submit a poster or abstract for ACOG or SMFM.

VI. Bibliography / References / Literature Cited

Reference:

1. Society for Maternal-Fetal Medicine and National Birth Equity Collaborative infographic, Strategies to Overcome Racism's Impact on Pregnancy Outcomes." Accessed June 16, 2022 at: https://s3.amazonaws.com/cdn.smfm.org/media/2315/Strategies_to_Overcome_Racism_Infographic.pdf.

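### The only publication route the protocol states is conditional on a successful result, and nothing commits the team to public reporting of a null or adverse one

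*Combined protocol and SAP*

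**What the plan says.** Section V.D (Publication Plan) is a single sentence. It opens "If successful in improving pregnancy care with an increase in perceived quality of care and reduction adverse pregnancy outcomes, we will use our results" and continues "to write a pilot study and submit a poster or abstract for ACOG or SMFM". It sets no threshold, test or margin for success, and it does not say what happens to the results otherwise.

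Three other places bear on reporting:

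- V.C promises, without a success condition, that "Participants will receive a letter with the study results".
- V.A says, also without condition, that "95% confidence intervals will be reported".
- The cover page carries a registration number, but the document gives no plan for posting results.

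On size, II.C states "Randomization will be 1:1 and will stop after reaching our desired sample size of forty total patients", with 20 in each arm. Despite its heading, that section gives no alpha, power, effect size, SD or event rate. V.A names the tests: "t-tests will be used to compare continuous variables and chi-squared tests will be used to compare categorical variables".

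**The concern.** When the decision to publish depends on the result, the published estimate is no longer drawn from all the results that the trial could have produced. It is drawn from the favourable ones, and their average is higher than the true effect. The smaller the trial, the wider the sampling distribution and the larger this shift. With 20 per arm the distribution is wide.

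Two things are at stake. First, readers would see an estimate that overstates the benefit on average, with nothing to show that it had been selected. Second, a null or adverse result, which is also evidence about doula care in this population, has no stated way of reaching anyone beyond the participants. Because success is undefined, whether the condition has been met can also be judged after the data have been seen.

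**Working it through.** **The plan's own figure.** The total of 40 cannot be reproduced, because none of the inputs to a sample-size calculation is given. The check therefore takes 20 per arm as fixed and asks how far selection on success would move the average published estimate.

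**Inputs**

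- From the protocol: 20 per arm (II.C); t-test for continuous outcomes and chi-squared test for categorical outcomes (V.A).
- Assumed: two-sided 5%, suggested by the 95% intervals in V.A; outcome SD of 1, so that effects are in SD units; true effects of 0.2, 0.3, 0.5 and 0.8 SD; and the event rates shown below.
- Success is read in two ways, because V.D does not define it: (a) favourable and significant; (b) favourable direction only.

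**Precision**

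- Standard error of the difference: √(2/20) = 0.316 SD.
- Smallest significant difference: t(0.975, 38 df) × 0.316 = 2.024 × 0.316 = 0.64 SD.
- Difference detectable with 80% power (normal approximation): (1.960 + 0.842) × 0.316 = 0.89 SD.

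Under reading (a), nothing below about 0.64 SD would normally be published, whatever the truth.

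**Reading (a).** 400,000 simulated trials per effect size, averaging the estimate over those with t > 2.024.

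**Reading (b).** This has a closed form: mean given a positive difference = d + SE × φ(d/SE)/Φ(d/SE). At d = 0.5, d/SE = 1.581, φ = 0.1143 and Φ = 0.9431. The mean is 0.5 + 0.316 × 0.1143/0.9431 = 0.538, and the ratio is 0.538/0.5 = 1.08.

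| True effect (SD) | (a) chance of success | (a) mean published | (a) ratio | (b) chance of success | (b) mean published | (b) ratio |
|---|---|---|---|---|---|---|
| 0.2 | 9% | 0.76 | 3.8 | 74% | 0.34 | 1.7 |
| 0.3 | 15% | 0.78 | 2.6 | 83% | 0.40 | 1.3 |
| 0.5 | 34% | 0.83 | 1.7 | 94% | 0.54 | 1.08 |
| 0.8 | 69% | 0.96 | 1.2 | 99% | 0.81 | 1.01 |

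With no true effect, reading (a) would publish 2.5% of trials, at a mean of 0.72 SD.

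**Binary outcomes.** V.D's condition also asks for fewer adverse outcomes, so the same selection acts on those. Exact binomial enumeration with an uncorrected chi-squared test, 20 per arm:

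- 30% v 20% (true difference 0.10): under (a), 11% chance and mean published difference 0.33, or 3.3 times; under (b), 71% chance and 0.166, or 1.7 times.
- 40% v 20% (true difference 0.20): under (a), 29% chance and 0.365, or 1.8 times; under (b), 89% chance and 0.230, or 1.15 times.

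**Sensitivity to losses.** If 20% were lost (an assumption), leaving 16 per arm, the ratios under (a) become 4.2, 1.8 and 1.3 at 0.2, 0.5 and 0.8 SD.

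**With unconditional reporting.** There is no selection on the result, so the expected reported difference equals the true difference (ratio 1.0). Precision is unchanged: the standard error is still 0.32 SD.

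**The case against.** The strongest reply is that V.D says what will happen if the study succeeds and does not say that publication happens only then. That stands. A reader might infer that a null or adverse result will be suppressed, but no section says so, and participants are promised the results in any case. The supportable statement is that a null result has no committed public route. The letter, the confidence intervals in V.A and the registration number do not supply one: the first goes to participants, the second describes the analysis, and the third comes with no posting plan.

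A second reply is that the large ratios depend on reading success as statistical significance, which V.D does not mention. That also stands, and it is why both readings are shown. If a favourable direction is enough and the true effect is 0.5 SD or more, the bias is small. A reader might also infer that whatever is published must be too large. That does not follow: the bias is in the average, and a single published estimate could lie below the truth.

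Third, I.B.3 makes the follow-on grant conditional too ("If our study is successful in showing these improvements in birth equity, we will submit an NIH"). A reader might infer that this adds to the bias, or that the larger study would be sized on an exaggerated effect. Neither is supported. Deciding whether to seek further funding after a pilot is an ordinary go/no-go step that does not alter this trial's estimate, and nothing says that the next study would be sized on this trial's point estimate.

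**Conclusion.** The point holds in this form: the one stated publication route depends on success, and public reporting of any other result is not committed. Following the plan as written selects publication on outcome and so biases the published effect upward on average. For the primary outcome, the size over the assumed true effects of 0.2 to 0.8 SD runs from almost nothing (1.01 times: direction only, 0.8 SD) to nearly fourfold (3.8 times: significance required, 0.2 SD). The document does not allow this range to be narrowed, because it defines neither success nor an expected effect. The direction of the bias does not depend on those assumptions. It is upward under both readings and at every effect examined. The trial can run without the change, but its public evidence should not depend on how the result falls.

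**What to change.** Replace the text of V.D with:

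> Results for the primary outcome and all four secondary outcomes will be reported with 95% confidence intervals and submitted for publication or presentation whatever their direction or significance.

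The four secondary outcomes are cesarean delivery, preterm birth, postpartum depression and breastfeeding. No change to the grant wording in I.B.3 is needed.

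The cost is one sentence of protocol wording and, if the result is null or adverse, the work of writing it up as an abstract or short report. Sample size, conduct and analysis are unaffected. The change removes the selection but does not make a 40-patient trial more precise, so the intervals will still be wide.

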APPENDIX I: VULNERABLE POPULATIONS

- I.** Research Coordinator will speak directly to the patient either in person or via telephone to explain the study, Doula enhanced care, and discuss interest in enrollment. Coordinator will go through the consent form with them, answer questions to satisfaction of the patient, and provide a copy to the patient, as well as contact information should they have questions later
- II. Cognitively or decisionally impaired individuals:** N/A
- III. Children:** N/A
- IV. Pregnant women:** Pregnant people are the focus of the study.
- V. Prisoners:** N/A
- VI. Students and/or Employees:** N/A
